1.0 Background

Current protocols used in clinical practice for stress echocardiography evaluation include exercise efforts (bicycle and treadmill) and pharmacologic stimulation. The pharmacologic stress echocardiography in the US is almost exclusively performed with Dobutamine.

In clinical practice vasodilator agents for stress testing have been limited for the use of perfusion imaging with nuclear isotopes. Nuclear stress testing is more expensive, equipment heavy, less available and much less portable than echocardiography imaging systems. It also exposes patients to a significant radiation dose (1).

Stress echocardiography is known for its comparable accuracy in detection of obstructive coronary artery disease when compared with nuclear methods. In a highly quoted pooled analysis of 18 studies in 1304 patients who underwent exercise or pharmacologic stress echocardiography in conjunction with thallium or technetium- labeled radioisotope imaging, sensitivity and specificity were 80% and 86% for echocardiography. Corresponding values were 84% and 77% for myocardial perfusion imaging, respectively (2).

The main limitation of stress echocardiography has been imaging quality and the fact that segmental dysfunction recognition depends on the human eye assessment of wall thickening (3). New, validated, ultrasound imaging technology now exists to aid in the recognition of segmental systolic dysfunction in more objective ways, namely the use of speckle tracking imaging(4). This technology uses the systolic tracking of speckles to define tissue deformation of the different cardiac segments in all the dimensions of cardiac, systolic, mechanical motion. The quality of this technology for precise segmental function analysis relies on the use of higher frame rates (5); which can be defeated in the case of tachycardia. Since a certain level of tachycardia is needed for accuracy in Dobutamine stress echocardiography testing (DSE), therefore combining DSE with speckle tracking imaging would be sub optimal. Speckle tracking imaging values in its longitudinal dimension has also proven more reliable for all-cause mortality prediction than more traditionally accepted measures such as Left Ventricular ejection fraction (LVEF) and wall motion score index (WMSI) (6).

The use of vasodilatation for stress echocardiography examination has been performed successfully in the past, also with the use of regadenoson, but for the

**Proprietary Information of MD Anderson  

## 2.0 Objectives

Primary objective: We aim at demonstrating that the angiogram (by either coronary angiography or coronary CT angiogram) and the regadenoson stress

**Proprietary Information of MD Anderson**  
**04-13-2021**

echocardiography (ReSTE) are equivalent in classifying ischemia among SPECT positive patients; this corresponds to test if ReSTE is as accurate as SPECT in the diagnosis of ischemia at least among SPECT positive patients (Grp 1).

Secondary aims: assess whether or not ReSTE adds predictive information above and beyond SPECT in predicting 30d post-operative cardiac events (Grp 2).

### 3.0 Patient Eligibility

#### **Inclusion Criteria:**

1. Cancer patients who are scheduled for (perfusion) nuclear stress testing using regadenoson as stress agent.
2. Indications for stress testing is either:
  - as part of a pre-operative evaluation prior to a planned cancer related surgery that is considered to be at least of intermediate risk (Intra-peritoneal, intra-thoracic, head and neck surgery, orthopedic or prostate surgery) **OR**
  - as part a cardiology evaluation for symptoms described in a cardiology consult as typical angina, or of significant suspicion for coronary disease or symptoms described as likely of a cardiac/coronary etiology.
3. Patients with a history of LV dysfunction will be still candidates for enrollment in the study if they have documented LVEF recovery (most recent documented LVEF of 50% or higher) for at least 6 months prior to SPECT regardless of current cardiac medication regimen.
4. Age 18 - 80 years.

#### **Exclusion Criteria:**

1. Patients consented for the trial that on the baseline 2D study have poor acoustic echo windows (i.e. a reader is unable to see in definition 2 or more segments from the apical views) will not be eligible to continue in the trial and peak hyperemia images will not be obtained.
2. Any patient with tachycardia defined as HR of 100 or higher at the day of SPECT will not be eligible for this study.
3. Second or third degree AV block.
4. Sinus node dysfunction.
5. Patients with allergy to regadenoson.
6. Patients with left bundle branch block (LBBB) and/or artificial pacemaker.

### 4.0 Research Plan and Methods

**Study Outline:**

Upon signed informed consent and enrollment, patients will be imaged during regadenoson infusion using the stated imaging protocol. If two contiguous segments in any of the apical views are not visible patients will not be registered in the study and will be entered in CoRE as screen failures due to eligibility criteria.

For ECHO, images will be stored for strain analysis in the ECHO PAC system and will be analyzed by a single blinded investigator ([name]). All strain will be obtained using the 2D strain analysis pathway. Global longitudinal strain (GLS), 2D LVEF with bi-plane Simpsons method of calculation, end diastolic volume (EDV bi-plane), end systolic volume (ESV bi-plane) and stroke volume (SV) values will be obtained and saved.

SPECT images will be interpreted by a blinded pool of faculty that includes radiologists and cardiologists from the institution. On those patients (Grp 2) who are studied pre-operatively the proposed surgery description and total surgical time will be recorded. Immediate post-op cardiac events (MACE) and 30 day post-operative cardiac events (MACE) will be recorded from inpatient records by chart review or if needed by telephone contact to patients. The post-operative events will be used to report prognostic accuracy of both testing methods and for comparison.

Patients who have coronary angiography or coronary CT angiograms will have the imaging data and test report data saved and stored for the final analysis (Grp 1).

The accuracy of both tests will be compared in those patients with angiogram data (Grp 1).

**Study Design:** Prospective comparison for demonstration of equivalence. Will attempt to show same specificity and sensitivity with ReSTE compared to SPECT at detecting (segmental/coronary) distribution defects.

**Study “treatment”:**

The only agent will be standard dose regadenoson for nuclear stress test; unchanged from our current protocol: “Regadenoson (5 mL, containing 0.4 mg of regadenoson) should be given as a rapid (approximately 10 seconds) injection into a peripheral vein using a 22 gauge or larger catheter or needle. Administer a 5 mL saline flush immediately after the injection of regadenoson.”

**Study Population:** The study population consists of cancer patients being evaluated with regadenoson nuclear stress tests for evaluation of chest pain or pre-operatively (cancer related surgery). We will concentrate on recruiting patients who are being evaluated pre-operatively for surgery that is considered to be at least of intermediate risk based on the American College of Cardiology Guidelines on Perioperative Cardiovascular Evaluation and Care for Non-

**Proprietary Information of MD Anderson**  
**04-13-2021**

cardiac Surgery (7); since a large number of patients that come for the test in our center are ordered to have perfusion stress test directly from the surgical or the pre-operative assessment clinics.

**Planned Study Duration:** Approximately 48 months. Given that approximately 900 patients come thru our department per year to get evaluation with SPECT but only approximately 300 will undergo catheterization, final timing depends on recruitment rate and volumes given our inclusion criteria items 2-3.

**Imaging Protocol:**

All ReSTE studies will be performed on GE systems (VIVID E9). Special attention will be given to avoid foreshortening.

The patients will be positioned on standard L recumbent position.

Transthoracic echocardiography will be performed using the Vivid E9 (GE Healthcare, Milwaukee, Wisconsin).

The same system will be used to acquire all echocardiograms. All echocardiograms will be analyzed in our laboratory. LVEF will be calculated from the apical 4- and 2-chamber views using a modified Simpson's biplane method by single investigator.

To measure myocardial strain, 2-dimensional grayscale images will be obtained in the parasternal short-axis view at the mid-papillary and apical levels; as well as the 3 standard apical views (apical 4-, 3- and 2-chamber views).

The timing of aortic valve closure will be obtained using pulsed-wave Doppler traces in the apical 3 or 5 views (using the more direct angle). Peak systolic radial and circumferential strain will be measured by averaging the peak systolic strain values in all 6 segments of the parasternal short-axis view (EchoPAC; GE Healthcare).

Summary of views: All ReSTE images will be obtained at rest and at peak hyperemia (between 2-4 min period post regadenoson injection).

1. Apical 4 view, at highest possible frame rate (>40fps)
2. Apical 3, at highest possible frame rate (>40fps)
3. Apical 2, at highest possible frame rate (>40fps)
4. Base SAX view, for torsion analysis
5. Apex SAX view (pass the insertion of the papillary muscles), for torsion analysis
6. One full 3D loop, at least 2 beats.
7. All images must be sent to ECHO-PAC system (internal disk).

In light of several publications (8,9) supporting the state of peak hyperemia with regadenoson at the 2-4 min after injection interval, including a study used

**Proprietary Information of MD Anderson  
04-13-2021**

for perfusion echocardiography (10), we will obtain these images after the 2nd minute and expect to complete by the 4th minute.

SPECT protocol will be performed as the current MDACC standard.

ReSTE will be performed concomitantly with SPECT as planned by ordering clinician. Therefore the same dose of regadenoson will be in effect used for both tests. We anticipate the potential need for ReSTE re-imaging of approximately 10% of participants to ensure that images are adequate for research quality measurements. In this event, an additional dose of regadenoson will be given after nuclear imaging is complete so that ReSTE peak hyperemia images can be redone.

**Data management and consent**

Consent will be obtained by designated personnel who will be well informed about the purpose of the study and potential risks prior to patient enrollment. Detailed information regarding the purpose of the study and potential risks will be discussed with the patient. An opportunity will be provided to patients to address any questions or concerns related to participation. Patients will be informed that participation is voluntary and consent and participation may be withdrawn at any time. Patients will also be informed that there is no compensation for participation.

Provisions taken to maintain confidentiality of specimens/data:

Unique study numbers will be assigned and all identifiers will be removed. Data will be stored in PDMS to ensure CFR Title 21 Part 11 compliance. Paper records will be kept locked in file cabinet and secured in locked office. Only study collaborators and Cardiology department personnel will have access to the data. Study records and data files will be disposed of in accordance to institutional policies after study is completed.

**Security plan for data:**

**Collection of Identifiers:**

Identifiers (name, medical record number) will be collected but will be replaced by study numbers. The key linking these numbers will be retained in a locked file by the investigator designated personnel.

**Breaking of Blind:**

The PI will remain blinded to the nuclear results obtained during the ReSTE until strain interpretation is completed to prevent bias. Breaking of the blind will not be necessary for safety as no clinical decision making will be based upon the strain results.

**Training of personnel:** Only MDACC personnel designated by the Principal investigator will have access to study records. These personnel will be fully trained to maintain the patient health information confidentiality.

**Data Storage:** Patient information and relevant data will be stored on password-protected institution computers behind the institution firewall. Data will not be transferred to laptop computers that are removed from the institution.

**Data Sharing:** Study data will not be shared with any individuals or entities that are not involved in the study.

**Final disposition of study records:** These data will be used only for this research study. Study data will be retained by the PI and will be disposed of in accordance to institutional policies after study is completed. No more than 5 years after manuscript publication.

**Sample Size:** 300 patients.

**Criteria for Removal (If indicated):** Any time, at patient request.

## 5.0 Reporting Requirements

### **Adverse Events**

All serious adverse events related to regadenoson will be documented and reported to Astellas Pharm Inc. The use of aminophylline as an antidote will be reserved for severe adverse events experienced due to regadenoson per MDACC protocol.

## 6.0 Statistical Considerations

### **Statistical analysis:**

Design and sample size/power

This is a 1-arm trial in cancer patients who are considered in the Department of Cardiology for stress testing. The primary objective of the study is to evaluate the ability of ReSTE (novel screening method) to identify patients with ischemia with as much accuracy as the conventional method, SPECT. Due to budgetary and other constraints (see below), the evaluation will be conducted among SPECT positive patients (Grp 1).

A total of 300 eligible patients will be enrolled into this trial. Each patient will undergo both SPECT and ReSTE stress testing for the diagnosis of ischemia. The gold standard test for the diagnosis of ischemia is angiography. However not all of the 300 patients will receive an angiogram due to patient's availability (many patients' primary concerns will be cancer related), current practice

## Proprietary Information of MD Anderson 04-13-2021

guidelines as well as financial limitations. Currently, only those who are SPECT positive may potentially receive an angiogram. We expect 210 (70%) of the 300 patients will be SPECT positive. Out of those 210 patients, 178 (85%) will actually undergo an angiography (Grp 1).

Since not all of the 300 patients will receive an angiogram, we will not be able to demonstrate directly the non-inferiority of ReSTE with regard to its accuracy of identifying ischemia when compared to SPECT imaging. However if ReSTE is truly as accurate as SPECT in its ability of identifying ischemia, then among those who are SPECT positive and also undergo an angiogram test, we expect minimum discordance between the angiogram and the ReSTE. Therefore, we aim at demonstrating that the angiogram and the ReSTE are equivalent in classifying ischemia among the SPECT positive patients; this corresponds to test if ReSTE is as accurate as SPECT in the diagnosis of ischemia at least among SPECT positive patients. Assuming that the true respective ischemia rates diagnosed by angiogram and ReSTE are  $P_0$  and  $P_1$ , we will perform equivalence test to test the following hypotheses:

$$H_0: |P_1 - P_0| > 0.05;$$

$$H_1: |P_1 - P_0| \leq 0.05;$$

If we observe a 7% discordance rate (equivalent to 12 of the 178 patients) between the angiogram and ReSTE results, and we were to allow a  $\pm 5\%$  tolerance limit, we would have 80% power to declare equivalence using a one-sided paired test of equivalence in proportion (alpha of 0.05), i.e. we will reject the null hypothesis that  $|P_1 - P_0| > 0.05$  and accept the alternative hypothesis that  $|P_1 - P_0| \leq 0.05$ . Lower discordance rates would yield higher power, so this estimate of power is rather conservative. The sample size calculation was performed using nQuery Advisor 7.0.

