## 7.0 Study Timeline

[figure not shown]
Our numbers are estimated based on the actual cardiac catheterizations performed in our lab. The cardiac catheterization lab opened in November 2009. It is the only full service cath lab in any cancer center. There were 250 angiograms performed in the first 12 months and the annual number has continued to increase annually. The percentage of angiograms performed in our cancer population is different than the population in any general cardiac center since our patients often find themselves in the position of needing a complete cardiac evaluation in order to proceed with anti-cancer therapies. Final disposition of the data: in accordance to MD Anderson institutional policies after the study is completed.

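### Does the department's 33% catheterization rate undermine the plan to obtain 178 angiograms from 300 enrolled patients?

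*Combined protocol and SAP*

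**What the plan says.** Section 6.0 (Design and sample size/power) fixes enrolment at 300 and derives Grp 1 in two steps. First, "We expect 210 (70%) of the 300 patients will be SPECT positive". Second, "Out of those 210 patients, 178 (85%) will actually undergo an angiography (Grp 1"). The same section says that, at present, angiography is open only to SPECT-positive patients.

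The power statement follows: "If we observe a 7% discordance rate (equivalent to 12 of the 178 patients) between the angiogram and ReSTE results", with a margin of 0.05 and a one-sided alpha of 0.05, power is given as 80%. It adds: "Lower discordance rates would yield higher power, so this estimate of power is rather conservative". The software is named (nQuery Advisor 7.0), but no formula or assumed true difference is printed.

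The Planned Study Duration paragraph of Section 4.0 says "approximately 900 patients come thru our department per year to get evaluation with SPECT but only approximately 300 will undergo catheterization", and continues that "final timing depends on recruitment rate and volumes given our inclusion criteria items 2-3".

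Section 7.0 (Study Timeline) says "Our numbers are estimated based on the actual cardiac catheterizations performed in our lab" and "There were 250 angiograms performed in the first 12 months and the annual number has continued to increase annually". It also remarks that the share of angiograms in this cancer population differs from that in general cardiac centers. Section 2.0 and the Study Outline in Section 4.0 accept either invasive coronary angiography or a coronary CT angiogram.

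**The concern.** Grp 1 is the primary analysis set, so the stated power depends on the product of two planning rates, 70% and 85%. The readable text derives neither. The one rate of catheterization per SPECT patient that can be read from it is little more than half the planned yield, and Section 7.0 says the planning numbers rest on catheterization volumes.

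Recruitment also concentrates on pre-operative patients, who enter before the SPECT result is known, and Section 6.0 itself lists reasons why some patients will not have an angiogram. With enrolment fixed at 300, a lower yield would leave fewer pairs and less power. The remark that the power is conservative addresses only the discordance rate, not the yield.

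**Working it through.** **1. The plan's own yield.** 300 × 0.70 = 210. Then 210 × 0.85 = 178.5, taken as 178. As shares, 178/210 = 84.8% and 178/300 = 59.3%. The multiplication is right.

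**2. The comparison rate (Section 4.0).** 300/900 = 33.3%. If that rate held for the enrolled patients and only SPECT positives were catheterized, it would mean 0.333/0.70 = 47.6% uptake, or 0.333/0.85 = 39.2% SPECT positivity. Either is far from the assumption in Section 6.0.

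**3. Are the two rates comparable?**

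| | Section 4.0, duration | Section 6.0, sample size |
|---|---|---|
| Denominator | All SPECT patients in the department, per year | Enrolled patients meeting the inclusion criteria |
| Numerator | Catheterization | Invasive or CT angiogram |
| Purpose | Recruitment timing | Size of Grp 1 |

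The duration sentence makes its own timing conditional on the inclusion criteria, so its volumes are counts before eligibility. Counting CT angiograms can only raise the yield, by an amount the documents do not give. Selection by indication could move it either way. The 250 angiograms in Section 7.0 have no SPECT denominator and give no rate.

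**4. Reproducing the power.** Inputs from Section 6.0: n = 178, discordance ψ = 0.07, margin 0.05, one-sided alpha 0.05. Assumed, because the plan does not state them: true difference zero and a normal approximation against one bound.

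Power = Φ(0.05 × √(n/ψ) − 1.645)

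At n = 178: 0.05 × √(178/0.07) = 2.521; 2.521 − 1.645 = 0.876; Φ(0.876) = 81.0%. This agrees with the stated 80%. The 12 discordant patients are 7% of 178 (12.46) rounded down; using 12/178 = 6.74% gives 82.2%.

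Pairs for 80% power on this formula: (1.645 + 0.842)² × 0.07/0.05² = 173.1, so 174.

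**5. Power at lower yields (ψ = 0.07, true difference zero, one bound).**

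| Pairs | Share of 300 | Normal approximation | Exact power, Tango test |
|---|---|---|---|
| 178 | 59.3% | 81.0% | 76.2% |
| 160 | 53.3% | 77.2% | 72.5% |
| 140 | 46.7% | 72.3% | 65.7% |
| 120 | 40.0% | 66.5% | 58.4% |
| 100 | 33.3% | 59.7% | 51.5% |

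The last row applies the department rate with no CT angiograms added. It is a low-end illustration, not a forecast.

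The break-even of 174 pairs belongs to the approximation. For the test named in the Analysis Plans, exact one-sided power is already below 80% at the full 178, so 174 is not a threshold for the planned analysis. Whether both equivalence bounds must be rejected is a separate question and is not examined here.

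**The case for a change.** The strongest case for acting is that the primary power claim rests on two unsourced rates, that the only related rate in view is much lower, and that there is little slack: on the approximation, 178 − 174 = 4 pairs. The source could be stated from existing departmental counts, with a short table of power by yield and no added patients.

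Much of this stands. The rates are not derived in the readable text, power at other yields is not shown, and the table above is not trivial at its lower end. Two things weaken it as a reason to change the plan. First, the absence of a derivation cannot be established: the timeline figure stands directly before the sentence on the basis of the numbers, Figure 1 survives only as a caption, and neither is shown. Second, the proposal has no corrected value to offer. It would keep or replace the 70% and 85% according to counts that are not in the documents. The small slack is also a weak argument: going from 174 pairs to 173 moves power only from 80.2% to just under 80.0%.

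**Conclusion.** No change follows. The 33% and the 59% measure different things, so neither shows the other to be wrong, and the documents support no better estimate of the yield.

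What remains is missing detail on where two planning rates come from. The cost if they prove optimistic is power alone: on the approximation, from 81% at 178 pairs to 72% at 140, and to 60% in the low-end case of 100. Fewer pairs make equivalence harder to declare. The margin, the nominal alpha and the paired method do not depend on the yield, so an equivalence finding would not become unsound for this reason. The analysts can report the Grp 1 size achieved and the interval it supports.

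This rests on an inferred formula with true difference zero, 7% discordance and one bound tested, and on treating content in the figures not shown as present in the plan. Counts of SPECT positivity and angiography in patients meeting the inclusion criteria could alter the view of the yield.

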### Analysis Plans

Patients' demographic and clinical characteristics will be summarized using descriptive statistics such as mean, standard deviation, median, interquartile range (IQR), frequency where appropriate. We will apply Student t-test/Wilcoxon test and Kruskal-Wallis test/ANOVA to compare continuous variables, and the chi-square test or the Fisher's exact test (14) to compare categorical variables in different patient groups (Grp 1).

As the primary analysis, we will use a paired test of equivalence for proportions proposed by Tango (11) to test the equivalence of the two ischemia tests among the SPECT positive patients.

Among the SPECT positive patients, Standard measures of clinical performance of ReSTE including sensitivity, specificity and positive and negative predictive values (12) will be estimated first. Additionally, the corresponding 2-sided 95% CI of binomial proportion will be calculated. We will use Receiver operating

characteristic (ROC) curve analysis (13) to assess the best cut-off for the ReSTE test, and calculate the area under the ROC curve to assess the performance of different cut-offs of ReSTE for the group.

For the secondary endpoints including cardiac event rates at Day 30 post-operation, we will provide estimates along with 95% confidence intervals (Grp 2). Univariate and multivariate logistic regression models will be fit to identify risk factors associated with the Day 30 events. Specifically, we will assess whether or not ReSTE adds predictive information above and beyond SPECT in predicting the Day 30 events. We hypothesize that patients who are positive on both SPECT and ReSTE have the highest Day 30 cardiac complication rates while those who are negative on both tests have the lowest cardiac complication rates. We will test whether the difference in statistical predictive accuracy between different logistic regression models (with or without ReSTE in the models) is significant (14). The predictive accuracy of the various logistic regression models will be quantified by C statistic, which provides the area under the receiver operating characteristics curve (13,14). To protect against over-fitting in the stepwise regression, we will use a bootstrap procedure to obtain an unbiased estimate of the C-index. These analyses will be performed using all patients for whom we have available data.

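### The stated 80% power to declare equivalence matches a test of one bound; for the two-bound hypothesis as written, the same inputs give about 52% to 62%

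*Combined protocol and SAP*

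**What the plan says.** The primary aim is equivalence, and the protocol says so consistently. Section 4.0 (Study Design) reads "Prospective comparison for demonstration of equivalence". Section 6.0 says "we aim at demonstrating that the angiogram and the ReSTE are equivalent in classifying ischemia among the SPECT positive patients", and then "we will perform equivalence test to test the following hypotheses": H0 is |P1-P0| > 0.05 and H1 is |P1-P0| ≤ 0.05, where P0 and P1 are the ischemia rates by angiogram and by ReSTE.

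The planning inputs are in the same part of section 6.0. The number of pairs comes from "Out of those 210 patients, 178 (85%) will actually undergo an angiography (Grp 1"). The discordance comes from "If we observe a 7% discordance rate (equivalent to 12 of the 178 patients) between the angiogram and ReSTE results". With a ±5% tolerance, the conclusion is that "we would have 80% power to declare equivalence using a one-sided paired test of equivalence in proportion (alpha of 0.05"), and the sentence goes on to define success as rejecting |P1-P0| > 0.05. The paragraph then adds: "Lower discordance rates would yield higher power, so this estimate of power is rather conservative". nQuery Advisor 7.0 is named, but neither the module nor a true value of P1-P0 is given.

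For the primary analysis, section 6.0 (Analysis Plans) states "we will use a paired test of equivalence for proportions proposed by Tango (11) to test the equivalence".

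**The concern.** A null hypothesis on the absolute difference is rejected only if the data exclude a difference of -0.05 or lower and also a difference of +0.05 or higher. Each component test is one-sided at 0.05, but both must succeed. When P1 = P0, each component can fail through a chance imbalance in its own direction, so the power for equivalence is well below the power of either component. A planning figure labelled one-sided and attached to a two-bound claim may therefore be the power of one component only.

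This is the primary hypothesis and the only one in the protocol with a power statement. If the true power is much lower, the trial is more likely than its readers expect to end without showing equivalence even when it holds, and that result could be misread as evidence against ReSTE. Calling the figure conservative adds to the risk, because only the favourable direction of error in the discordance rate is mentioned.

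**Working it through.** **Inputs** (all from section 6.0 unless noted)

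- n = 178 pairs
- discordance ψ = 0.07, equated in the text with 12/178 = 0.0674
- margin 0.05 in each direction
- one-sided alpha 0.05 per bound, so z = 1.645
- true difference P1-P0: not stated; taken as 0, with other values shown below

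**Step 1. Reproduce the 80%: one bound, normal approximation**

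With P1 = P0, the standard error of the paired difference is √(ψ/n) = √(0.07/178) = 0.01983, and 0.05/0.01983 = 2.521.

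Power for one bound = Φ(2.521 - 1.645) = 0.810.

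The number of pairs for 80% power on one bound is 0.07 × (1.645 + 0.842)²/0.05² = 173.1, so 174, close to the planned 178. The stated figure is reproduced.

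**Step 2. Both bounds, same inputs**

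Power for both = 2 × Φ(2.521 - 1.645) - 1 = 2 × 0.8096 - 1 = 0.619.

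**Step 3. Exact calculation**

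Let b and c be the two discordant counts. Power is the trinomial probability, summed over all (b, c), that the statistic at -0.05 exceeds 1.645 and the statistic at +0.05 is below -1.645. Two statistics were used, with Δ the bound:

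- Wald: (b - c - nΔ)/√(b + c - (b - c)²/n)
- Tango score: (b - c - nΔ)/√(n(2q + Δ(1 - Δ))), with q the maximum likelihood estimate of the c-cell probability under the restriction that the difference equals Δ

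| Method (P1 = P0) | One bound, ψ = 0.07 | Both bounds, ψ = 0.07 | Both bounds, ψ = 12/178 |
|---|---|---|---|
| Normal | 81.0% | 61.9% | 64.5% |
| Exact Wald | 80.1% | 60.1% | 62.6% |
| Exact Tango (planned test) | 76.2% | 52.5% | 54.8% |

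**Step 4. The protocol's own count of 12 discordant pairs**

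Here nΔ = 178 × 0.05 = 8.9.

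- Split 5/7, weaker bound: Wald (-2 + 8.9)/√(12 - 4/178) = 1.994; Tango 1.768. Both exceed 1.645.
- Split 4/8, weaker bound: Wald (-4 + 8.9)/√(12 - 16/178) = 1.420; Tango 1.294. Both fail.

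Only the splits 5/7, 6/6 and 7/5 clear both bounds, under either statistic. If P1 = P0, the split is binomial(12, 0.5):

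- one bound: P(at least 5) = 3302/4096 = 80.6%
- both bounds: P(5 to 7) = (792 + 924 + 792)/4096 = 2508/4096 = 61.2%

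This step needs no normal approximation for the power. The 80% again appears only for one bound.

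**Step 5. Other two-bound variants at n = 178**

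- null variance, normal: 63.5% to 67.0%
- continuity correction: 44.7% to 47.5%
- alpha 0.025 per bound, normal, ψ = 0.07: 42.5%

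None reaches 80%.

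**Step 6. Sensitivity, exact Tango, both bounds, n = 178**

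The discordance rates other than 7% are illustrative and do not come from the protocol.

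| Discordance (P1 = P0) | 4% | 5% | 7% | 10% | 12% | 15% | 20% |
|---|---|---|---|---|---|---|---|
| Power | 80% | 71% | 52% | 28% | 16% | 6% | 0.4% |

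| True difference at 7% discordance | 0 | 0.01 | 0.02 | 0.03 |
|---|---|---|---|---|
| Power | 52% | 48% | 36% | 23% |

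**Step 7. Pairs for 80% power on both bounds at 7% discordance**

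- Normal: 0.07 × (1.645 + 1.282)²/0.05² = 239.8, so 240 pairs.
- Exact Tango: 269 pairs gives 80.7%. At the planned yield of 70% × 85% = 59.5%, that is 269/0.595 = 452.1, so about 453 enrolled.

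**The case against.** The strongest defence is that the sentence itself says one-sided and that the nQuery settings are not shown, so the cause of the mismatch cannot be proved. That is fair on cause: a numerical match is strong evidence of a one-bound calculation, not proof. It does not save the figure, because the same sentence attaches the 80% to rejecting |P1-P0| > 0.05, and no two-bound calculation tried gives 80% from the stated inputs.

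A second point is that 52% is the lowest of the main figures. Using 12/178 in place of 7% gives 54.8% with Tango and 64.5% by normal approximation; conditioning on exactly 12 discordant pairs gives 61.2%. Part of the fall to 52% reflects the exact Tango calculation rather than the missing bound. This stands, and it is why a range is reported. The missing bound alone costs about 19 to 24 points within any one method (81.0 to 61.9, 80.1 to 60.1, 76.2 to 52.5).

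Third, the higher discordance rates in the sensitivity table have no source in the protocol. True: they show how steeply power falls and are not evidence of what will occur.

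Finally, the error concerns planning only. The Tango test is specified separately, so the type I error and the meaning of a positive result are unaffected. That also stands; what is at risk is an inconclusive primary result.

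**Conclusion.** The concern holds. With 178 pairs, 7% discordance, a ±0.05 margin and alpha 0.05 per bound, the power to declare equivalence is about 62% by normal approximation and about 52% by exact calculation with the planned test, not 80%. The chance of missing a true equivalence is 38% to 48%, not 20%. Reading the discordance as 12/178 moves the range only to 55% to 65%.

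The result rests on P1 = P0, which the protocol does not state. It is the best case: any true difference within the margin lowers two-bound power further. The description of the 80% as conservative is not supported, since higher discordance or any true difference reduces power and only lower discordance raises it. Because this is the only power claim in the protocol and it belongs to the primary hypothesis, it must be corrected.

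**What to change.** In section 6.0 (Design and sample size/power), replace the power sentence with wording such as: *With 178 pairs, 7% expected discordance and no true difference (P1 = P0), two one-sided 0.05 Tango tests against -0.05 and +0.05 give about 52% power by exact enumeration (about 62% by normal approximation).* Delete the remark that the estimate is conservative. Add a small table of exact Tango power by discordance, for example 7%, 10%, 15% and 20% (52%, 28%, 6% and under 1%). State the assumed true difference and the software module and settings.

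This costs wording and one table; it adds no patients or procedures, but the stated power becomes less favourable. It corrects the text and leaves the design at that power. If 80% is wanted, the sponsor must either plan for about 269 pairs (about 453 enrolled at the planned yield, against 300) or justify a discordance of about 4%.

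Restating the hypothesis as one-sided is not recommended. It would give 76% (exact Tango) to 81% (normal) under P1 = P0, but it would abandon the equivalence aim, and against a gold standard it would leave either over-calling or under-calling by ReSTE without a limit.
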